2.3 Patient disposition, demographics and other baseline characteristics

Analyses on demographics, eligibility criteria, baseline disease characteristics, and other baseline data like medical history and prior treatments will not be repeated for the final CSR. The only analyses that need to be updated for the final CSR Section 14.1 are the tables on disposition and protocol deviations, as well as analysis sets.

The Full Analysis Set (FAS) will be used for all baseline and demographic summaries and listings unless otherwise specified. Summaries will be reported by Age group and for all patients, and listings will be reported by Age group to assess baseline comparability. No inferential statistics will be provided.

Basic demographic and background data

All demographic and baseline disease characteristics data will be summarized and listed by Age group. Categorical data (e.g. gender, race, ethnicity) will be summarized by frequency counts and percentages; the number and percentage of patients with missing data will be provided. Continuous data (e.g. age, weight, height, body surface area, body mass index) will be summarized by descriptive statistics (N, mean, median, standard deviation, minimum and maximum).

Diagnosis and extent of disease

Summary statistics will be tabulated for diagnosis and extent of disease in underlying disease, stem cell transplant and chronic GvHD.

For underlying disease, the analysis will include the following: primary diagnosis category and subcategory, details of primary diagnosis, time since diagnosis of underlying disease, CIBMTR risk assessment.

For transplant related disease history, the analysis will include the following: conditioning regimen type, total HCT-specific comorbidity index score, time since transplant, time from diagnosis of underlying disease to transplant, stem cell type, donor information including age, gender, HLA typing method, HLA match score, source of grafts (HLA matched related donor, unrelated UCB (umbilical cord blood), related haploidentical, HLA matched/mismatched URD (unrelated donor)), T-cell depleted (Y/N), total nucleated cell dose.

For cGvHD disease history, the analysis will include the following: prior diagnosis of aGvHD, time since initial diagnosis of cGvHD, overall severity of initial cGvHD, cGvHD severity at baseline (study entry), time since steroid refractory cGvHD, cGvHD organ involvement, steroid dose at baseline (study entry).

Medical history

Medical history and ongoing conditions, including underlying disease conditions and symptoms entered on eCRF will be summarized and listed by Age group. The summaries will be presented by primary system organ class (SOC), preferred term (PT) and Age group. Medical history and current medical conditions will be coded using the Medical Dictionary for Regulatory Activities (MedDRA) terminology. The MedDRA version used for reporting will be specified in the CSR and as a footnote in the applicable tables/listings.

Other

All data collected at baseline including Tanner Staging will be listed.

2.3.1 Patient disposition

Enrollment by country and center will be summarized for all screened patients and also by Age group and for all patients. The number (%) of treated patients will be presented overall and by Age group. The number (%) of screened and not-treated patients and the reasons for screening failure will also be displayed. The number (%) of patients in the FAS who are still on treatment, who discontinued the treatment phases as well as the reason for discontinuation, and the long term follow-up will be presented overall and by Age group.

Protocol deviations

The number (%) of patients in the FAS with any protocol deviation will be tabulated by deviation category overall and by Age group for the FAS. All protocol deviations will be listed.

To assess the impact of COVID-19 pandemic on the conduct of the study, COVID-19 specific protocol deviations will be summarized and listed separately.

Analysis sets

The number (%) of patients in each analysis set (defined in [Section 2.2](#)) will be summarized by Age group.

2.4 Treatments (study treatment, rescue medication, concomitant therapies, compliance)

2.4.1 Study treatment / compliance

Duration of exposure to ruxolitinib will be summarized by Age group and by means of descriptive statistics. It will also be categorized into time intervals; frequency counts and percentages will be presented for the number (%) of patients in each interval.

Total daily dose, actual cumulative dose, dose intensity (DI) and relative dose intensity (RDI) will be summarized for ruxolitinib by Age group.

The number (%) of patients who have dose reductions or interruptions, and the reasons, will be summarized for ruxolitinib by Age group.

Patient level listings of all doses administered on treatment along with dose change reasons will be produced by Age group.

The Safety Set will be used for all summaries and listings of study treatment.

If more than one dose and/or formulation is assigned within one Age group, then summaries and listings will be reported by Age group as well as doses/formulation within the Age group

Duration of follow-up

The duration of follow-up time is defined as (date of last contact) – (date of first administration of investigational treatment) + 1.

Duration of exposure to investigational treatment

Duration of exposure to investigational treatment (days) = (last date of exposure to investigational treatment) – (date of first administration of investigational treatment) + 1.

If any subjects tapered off ruxolitinib and re-started ruxolitinib treatment due to cGvHD recurrence, two different definitions of duration of exposure will be distinguished:

- **Duration of exposure including taper off periods** is defined as the time from first to very last date of ruxolitinib treatment, which includes the intervening period without treatment.
- **Duration of exposure excluding taper off periods** is defined as above but deduct the intervening period without treatment for subjects who taper off and restart after cGvHD recurrence. These periods are captured as dose interruption with reason “dose tapering following response”.

Summary of duration of exposure of investigational treatment in days will include categorical summaries (based on clinically meaningful time intervals) and continuous summaries (i.e. mean, standard deviation etc.) using appropriate units of time.

Duration of exposure to investigational treatment in patient-years

The duration of exposure to investigational treatment in patient-years is a total of the duration of exposure to investigational treatment in years from all the patients in the Age group.

Duration of exposure to systemic corticosteroid

Duration of exposure to systemic corticosteroid treatment (days) = (last date of exposure to systemic corticosteroid) – (date of first administration of systemic corticosteroid) + 1.

Duration of exposure to systemic corticosteroid in patient-years

The duration of exposure to systemic corticosteroid in patient-years is a total of the duration of exposure to systemic corticosteroid in years from all the patients in the Age group.

Cumulative dose

The **planned cumulative dose** for ruxolitinib refers to the total planned dose per protocol up to the last dose date.

The **actual cumulative dose of ruxolitinib** refers to the total actual dose of ruxolitinib as documented in the Study Treatment eCRF.

For patients who did not take any drug the cumulative dose is by definition equal to zero.

Dose intensity and relative dose intensity of ruxolitinib

Subjects receive ruxolitinib in doses twice a day (bid). For purposes of reporting dose intensity, a summary over the dose by day (total daily dose) is provided.

Dose intensity (DI) of ruxolitinib for patients with non-zero duration of exposure is defined as follows:

$DI \text{ (mg / day or mg/m}^2\text{/day)} = \text{Actual cumulative dose (mg or mg/m}^2\text{) of ruxolitinib / Duration of exposure to ruxolitinib (days)}$.

In case the study includes subjects who taper off ruxolitinib and later re-start ruxolitinib treatment due to cGvHD recurrence, the duration of exposure excluding “taper off periods” will be used as denominator for dose intensity.

For patients who did not take any drug, the DI is by definition equal to zero.

Planned dose intensity (PDI) is defined as follows:

$PDI \text{ (mg/day or mg/m}^2\text{/day)} = \text{Planned Cumulative dose (mg or mg/m}^2\text{) / Duration of exposure (days)}$.

The PDI of ruxolitinib with daily dose schedule is according to protocol for the three age groups:

- Age group 1: 20 mg/day
- Age group 2: 10 mg/day
- Age group 3: 8 mg/m²/day using the baseline BSA

Relative dose intensity (RDI) is defined as follows:

$RDI = DI \text{ (mg / day or mg/m}^2\text{/day)} / PDI \text{ (mg / day or mg/m}^2\text{/day)}$.

The total daily dose, actual cumulative dose, DI and RDI up to last date of exposure to study treatment will be summarized.

Dose reductions, interruptions or permanent discontinuations

The number of patients who have dose reduction, or interruptions, and the reasons, will be summarized for ruxolitinib by Age group. Separate summaries will be generated for patients with dose change due to dose tapering (change of dose due to efficacy of treatment) and patients with dose change due to other reasons (potential safety concerns). The number of patients who have dose permanent discontinuations and the reasons will be summarized by Age group.

‘Type of change’ and ‘Dose permanently discontinued’ fields from the Study Treatment CRF pages will be used to determine the dose change, dose interruptions, and permanent discontinuations respectively.

The corresponding fields ‘Reason for Change’ and ‘Reason for Permanent Discontinuation’ will be used to summarize the reasons.

For the purpose of summarizing interruptions and reasons, in case multiple entries for interruption that are entered on consecutive days with different reasons will be counted as separate interruptions. However, if the reason is the same in this mentioned multiple entries on consecutive days, then it will be counted as one interruption.

Dose Reduction: A dose changed when the actual total daily dose is lower than the previous actual total daily dose A dose change due to dose tapering (change of dose due to efficacy of treatment) will not be considered as a dose reduction. Only dose changes that are indicated on the CRF as due to reason other than dose tapering, are taken into consideration. Number of reductions will be derived programmatically based on the change and the direction of the change.

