6.1.1 Investigational and control drugs

Table 6-1 Dose and treatment schedule

Investigational treatment	Age groups	Pharmaceutical form and Route of Administration	Dose	Frequency and/or Regimen
Ruxolitinib (INC424)	Group 1 ≥ 12 years old to < 18 years old	5 mg tablet* for oral use OR oral pediatric formulation	10 mg BID (2 tablets orally BID) OR 10 mg BID oral pediatric formulation**	Twice per day
Ruxolitinib (INC424)	Group 2 ≥ 6 years old to < 12 years old	5 mg tablet* for oral use OR oral pediatric formulation*	5 mg BID (1 tablet orally BID) OR 5 mg BID oral pediatric formulation**	Twice per day

Investigational treatment	Age groups	Pharmaceutical form and Route of Administration	Dose	Frequency and/or Regimen
Ruxolitinib (INC424)	Group 3 ≥ 2 years old to < 6 years old	5 mg tablet* for oral use OR oral pediatric formulation	4 mg/m ² BID (either tablet orally OR oral pediatric formulation)**	Twice per day
Ruxolitinib (INC424)	Group 4 ≥ 28 days to < 2 years old	oral pediatric formulation	X mg/m ² BID (oral pediatric formulation)** To be defined from study CINC424F12201	Twice per day

*A whole tablet for oral use may be crushed as per instructions in the pharmacy manual (if calculated dose based on BSA is not 5 mg or 10 mg, then crushing is not permitted. Tablet cannot be broken to achieve partial doses. In this case, oral pediatric formulation should be administered). Oral pediatric formulation should be dispensed according to instructions in the pharmacy manual.
Note: Crushed tablet(s) can only be administered orally and cannot be administered by nasogastric (NG) tube.
**Calculated doses should be rounded to the nearest available volume as per instructions in the pharmacy manual

The Investigator will instruct the subject to take the investigational treatment as per protocol.

All dosages prescribed and dispensed to the subject and all dose changes during the study must be recorded on the Dosage Administration Record electronic case report form (CRF).

Ruxolitinib will be administered orally twice per day at the assigned dose based on age group, given as 5 mg tablets or equivalent dose as oral pediatric formulation.

Ruxolitinib (tablet or oral pediatric formulation) should be taken approximately 12 hours apart (morning and night) without regards to food. Ruxolitinib will be administered by Investigator or delegate, or self-administered by the subject or parent/legal guardian in an outpatient setting.

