Subjects should be instructed not to take ruxolitinib at home on the days of the scheduled pre-dose blood collection for PK and biomarker samples. Refer to [Section 8.5.1](#) and [Section 8.5.2](#). Dosing will be administered after pre-dose blood collection at these visits.

If a dose is vomited within any timeframe after dosing, re-dosing should not occur.

If a dose is missed, the subject should not take an additional dose, but should take the prescribed dose at the next scheduled dosing time.

The ruxolitinib dose as assigned on Cycle 1 Day 1 (based on age) must **not** be changed until the subject completes the Cycle 7 Day 1 visit assessments, unless dose adjustments are needed to manage safety events. After Cycle 7 Day 1, the Investigator must re-evaluate the assigned ruxolitinib dose based on the subject's age and/or growth. Dosing based on growth should be adjusted if the newly calculated dose is a > 10% change from the previously calculated dose. Subjects should remain on the same formulation until Cycle 7 Day 1. Any change in formulation prior to Cycle 7 Day 1 requires approval from the Sponsor. All dose changes must be recorded on the Dosage Administration Record electronic case report form (eCRF).

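### Planned dose intensity stays at the entry dose although the protocol re-evaluates dosing after Cycle 7 Day 1, so relative dose intensity can exceed 1 in compliant children, mainly in Group 3

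*SAP*

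**What the plan says.** SAP 2.4.1 states that the planned cumulative dose "refers to the total planned dose per protocol up to the last dose date". PDI is that quantity divided by duration of exposure, and RDI is actual dose intensity (DI) divided by PDI. The SAP then gives PDI as constants: "Age group 1: 20 mg/day", "Age group 2: 10 mg/day" and "Age group 3: 8 mg/m²/day using the baseline BSA". RDI is summarised up to the last date of exposure, and nothing in the section updates PDI for age or BSA.

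Protocol 6.1.1 holds the Cycle 1 Day 1 dose until the Cycle 7 Day 1 assessments are complete, apart from safety adjustments. After that "the Investigator must re-evaluate the assigned ruxolitinib dose based on the" child's age and/or growth, and growth-based dosing should be adjusted when the newly calculated dose differs by more than 10% from the previous one. Planned treatment is 39 cycles of 28 days (Protocol 6.1.5 and 8.2.1).

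Three further statements bear on age. Protocol section 3 and SAP 1.1 keep each child in the age group of treatment start. Protocol 6.5.1 caps the dose at the starting level for the child's age group, without saying whether that means entry age or current age.

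**The concern.** After Cycle 7 Day 1 the numerator of RDI follows any re-assigned dose, while the denominator stays at the entry dose. For a child whose dose was re-assigned, the constants then no longer equal the planned dose per protocol, so the SAP's general definition and its listed values disagree.

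At stake is how the exposure tables in the final study report are read. They cover up to three years of treatment in growing children. An RDI above 1 would suggest more drug than planned in a child dosed exactly as the protocol directs. Where the assigned dose has risen, a shortfall against the new dose could be partly absorbed by the outdated denominator.

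**Working it through.** **The plan's own figures.** Table 6-1 gives 10 mg, 5 mg and 4 mg/m² twice daily for Groups 1, 2 and 3. Doubling gives 20 mg, 10 mg and 8 mg/m² per day. The SAP constants are therefore exactly the starting doses.

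**Inputs from the documents.** The dose is held for 6 × 28 = 168 days. Full treatment is 39 × 28 = 1092 days, leaving 1092 − 168 = 924 days after the hold. Enrolment was 22, 17 and 7 in Groups 1, 2 and 3 (46 in total; Protocol, Amendment 2).

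**Assumptions.** The documents give no BSA or growth values, so those below are illustrative. Every dose is taken, and rounding to available volumes is ignored. Growth is applied in one step from day 168, the earliest possible date, so each figure is an upper value for that total growth.

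**Group 3, growth only.** Let g be the proportional rise in the calculated dose, and let actual dose be normalised to baseline BSA. Then RDI = [168 + 924 × (1 + g)] / 1092.
- g = 0.11: (168 + 1025.64) / 1092 = 1.09
- g = 0.20: (168 + 1108.8) / 1092 = 1.17
- g = 0.30: (168 + 1201.2) / 1092 = 1.25
- BSA from 0.65 to 0.80 m² (ratio 1.231): (168 + 924 × 1.231) / 1092 = 1.20
- g of 0.10 or less: no adjustment is triggered, so RDI = 1.00

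Over 13 cycles (364 days), growth of 11%, 20% and 30% gives 1.06, 1.11 and 1.16.

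**Age-band crossing, conditional on current age governing the dose.** For a Group 2 child moved from 10 to 20 mg/day at day s, DI = [10s + 20(1092 − s)] / 1092 and RDI = DI / 10.
- s = 168: 20160 / 1092 = 18.46 mg/day, RDI 1.85
- s = 364: 16.67 mg/day, RDI 1.67
- s = 546: 15.00 mg/day, RDI 1.50
- s = 728: 13.33 mg/day, RDI 1.33

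For a Group 3 child moved to 10 mg/day at day 168 with baseline BSA B, RDI = [168 × 8B + 924 × 10] / (1092 × 8B). With B = 0.6, 0.7 and 0.8 m² (assumed), this gives 1.92, 1.67 and 1.48.

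**Masking, under the same condition.** Suppose the Group 2 child is re-assigned to 20 mg/day at day 168 but actually receives 10 mg/day throughout. The fixed PDI gives RDI = 1.00. Against a plan that follows the assignment, RDI = 10920 / 20160 = 0.54.

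With a planned dose that follows age and growth re-assignments, every fully compliant case above gives RDI = 1.00.

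**The case against.** The strongest reply is that RDI against the starting dose is a legitimate convention. SAP 2.4.2.3 uses it explicitly for corticosteroids, and Protocol 12.3 asks only for dose intensity. That stands as far as it goes, but for ruxolitinib the SAP calls the reference the planned dose per protocol, so the present label and content do not match.

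A second reply is that Group 3 DI, expressed in mg/m²/day, could use the BSA current at dosing, which would bring RDI close to 1 for growth alone. The SAP names only baseline BSA, and names it beside PDI. It does not say which BSA converts the actual dose, so the Group 3 figures depend on that reading and the text needs clarifying either way.

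Third, RDI is not the only view of dosing. Dose reductions are derived from the previous actual daily dose, interruptions and reasons are tabulated, all doses are listed, and failure to take the assigned dose and non-compliance are coded deviations. SAP 2.4.1 also adds summaries by dose where more than one is assigned within an age group. These stand and limit masking considerably, but none of them changes the RDI denominator.

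A reader might infer that RDI near 1.85 is the expected result for Group 2. The documents do not support that. The figure needs a switch immediately after Cycle 7 Day 1, full dosing to the end with no taper or discontinuation, and a reading under which current age sets the dose. If the cap in Protocol 6.5.1 refers to the entry group, the band-crossing and masking examples fall away.

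**Conclusion.** The inconsistency is real and its scope is narrow. The constants in SAP 2.4.1 are starting doses, and they stop matching the planned dose per protocol once a dose is re-assigned for age or growth.

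The firm part is Group 3, 7 of 46 enrolled, and within it only children whose calculated dose changed by more than 10%. Their RDI would be about 1.09 to 1.25 over 39 cycles for 11% to 30% growth, if actual dose is normalised to baseline BSA. The band-crossing part, about 1.3 to 1.9, could reach some of the 24 of 46 in Groups 2 and 3. It remains conditional until Protocol section 3, 6.1.1 and 6.5.1 and SAP 1.1 are reconciled; no view is taken here on which rule is right. The documents do not say how many children had a dose re-assigned.

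It would be wrong to infer that all three constants are affected. Group 1 has a flat dose in the top age band, so neither growth nor moving to a higher band alters its plan. It would also be wrong to infer an effect on efficacy: the primary endpoint at Cycle 7 Day 1 precedes re-evaluation, and no efficacy endpoint uses RDI. The consequence is confined to descriptive exposure reporting.

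**What to change.** Define the planned cumulative dose piecewise: the entry dose up to Cycle 7 Day 1, then the protocol-assigned dose in force on each day. Update it only for age or growth re-assignments. For growth, use the BSA at the last re-evaluation that met the 10% rule; using current BSA at every visit would make a child correctly left on the previous dose look underdosed. Do not update it for safety reductions, interruptions or response tapers, or the denominator will follow the very departures that RDI should show. Use the recorded reason for change to separate these, and check that age or growth can be identified from that field.

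State that the same BSA is used for DI and PDI in Group 3. Reconcile the protocol and SAP statements on age group and dose before programming the age component.

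At a minimum, label the present measure as relative to the starting dose and add RDI up to Cycle 7 Day 1, where starting dose and plan coincide.

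The cost is SAP wording and programming. Height, weight, derived BSA and dose-change records are already collected.

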2.4.2 Prior, concomitant and post therapies

Analyses on prior treatments or prophylaxis will not be repeated for the final CSR.

2.4.2.1 Prior prophylaxis

The number and percentage of patients who received any prophylaxis (e.g. CNI) prior to start of study treatment will be summarized by lowest ATC class, preferred term and group using FAS.

Listings will be generated for prophylaxis.

2.4.2.2 Systemic corticosteroid prior to start of study treatment

The number and percentage of patients who received systemic corticosteroids prior to study start will be summarized by Age group with number of days on steroids and peak daily dose, where doses of methylprednisolone will be converted to prednisone equivalents (see Section 2.4.2.3).

2.4.2.3 Systemic corticosteroid during study treatment

As per protocol the steroid doses of methylprednisolone will be converted to prednisone equivalents by multiplying the methylprednisolone dose by 1.25. Prednisone doses for each subject are converted to mg/kg/day.

The duration of exposure will be summarized for systemic corticosteroid by Age group and disease history of treatment naive-cGvHD or SR-cGvHD at baseline. It will be categorized into time intervals; frequency counts and percentages will be presented for the number (%) of patients in each interval. The actual cumulative dose, dose intensity and relative dose intensity (relative to the starting dose of corticosteroids) will be summarized up to the Cycle 7 Day 1 visit. Graphical display (box plots) will also be generated. These analyses will be based on Safety Set.

For the final CSR these analyses will be done considering data up to end of study/LPLV date.

